6.1. Statistical Methods

The methodology presented below is a summary of the more detailed analysis plan that will be presented in the Statistical Analysis Plan (SAP). The SAP will be finalized before the database is locked and unblinded. Any changes to the methods described in the final SAP will be described and justified in the clinical study report.

All statistical processing will be performed using SAS® (Version 9.4) unless otherwise stated.

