1. The first step is to understand the pattern of missingness. In order to perform the multiple imputation, a monotone missing pattern has to be achieved. For example, if there exist values for baseline and Week 4 visits, but missing values for the Week 1 or 2 visits, the Markov-Chain Monte-Carlo (MCMC) method will be used to impute the small amount of missing data that may be missing at the intermediate visits that is required to make the missing data pattern monotone before applying the multiple imputation algorithm. This method uses a non-informative Jeffreys prior to derive the posterior mode from the expectation-maximization (EM) algorithm as the starting values for the MCMC method. The MCMC method will use the seed 6457149. The vIGA-AD score will be treated as a continuous variable for this step and the model will include the vIGA-AD scores at baseline, Week 1, Week 2, and Week 4. To avoid values that could not be observed in practice, imputed values will be rounded to the nearest integer (Round=1 option in PROC MI) in the range of 0 to 4.

To determine the number of multiply-imputed datasets to be created at this step, the proportion of datapoints with non-monotone pattern across all visits and subjects will first be derived as follows:

$$\frac{\text{number of non monotone visits accross all visits and subjects}}{\text{total number of expected visits across all subjects}} * 100$$

Then, the following table will be used:

	STATISTICAL ANALYSIS PLAN, Version 3.0
Protocol Number: ARQ-151-311	Sponsor: Arcutis Biotherapeutics, Inc.

Non-monotone Missing Data	Number of Imputed Datasets
$\leq 2\%$	1
$> 2\% \text{ to } \leq 5\%$	3
$> 5\%$	10

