2. Once the monotone pattern is achieved, the next step is to implement the imputation algorithm. For this, the PMM regression method will be used. This method is particularly helpful if the normality assumption is violated. For subjects with complete data up to a particular visit, a PMM regression model will be fit that includes the outcome at that visit as the dependent variable and as independent variables, the treatment group, pooled study site, and vIGA-AD score outcomes at previous visits, using a seed of 482371. For other scales/questionnaires, the actual baseline vIGA score will also be included as an independent variable. This process will be repeated 25 times, resulting in a total of 25 to 250 complete analysis datasets, depending on the number of imputed monotone datasets that are required. The seed may be changed after unblinding in case of any issues with the imputation process, and it will be documented in the CSR if any change is required.
3. For each of the 25 to 250 completed dataset, the necessary derived variable will be computed as defined in Section 5.5 and analyzed using a CMH analysis, adjusted for the pooled study site and randomized vIGA-AD score for the primary efficacy endpoint and adjusted for the pooled site for the secondary efficacy endpoint. Results will be combined into one multiple imputation inference as follows:
 - a. Common proportion of success, common Mantel-Haenszel (MH) proportion difference (and associated 95% CI), and common MH odds ratio (and associated common 95% CI) will be combined using PROC MIANALYZE based on Rubin's rule. Common MH odds ratios and associated common 95% CI will first be normalized using a log-transformation before being combined using PROC MIANALYZE. The resulting combined common MH odds ratio and associated combined common 95% CI will be back-transformed to the arithmetic scale before being presented in a table.
 - b. For the combined common proportion of success, the associated combined common 95% CI will be calculated as per Lott and Reiter multiple imputation Wilson interval method¹.
 - c. Two p-values will be produced for each analysis:
 - i. The primary p-value will be obtained from a multiple imputation CMH test, where CMH general association statistics and their standard errors obtained

	STATISTICAL ANALYSIS PLAN, Version 3.0
Protocol Number: ARQ-151-311	Sponsor: Arcutis Biotherapeutics, Inc.

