from the analysis of each multiply-imputed dataset will be transformed as per Wilson-Hilferty² before being combined using PROC MIANALYZE based on Rubin's rule. Because the Wilson-Hilferty transformation is a monotone transformation, the p-value for the CMH test is the one-sided p-value from the t distribution. This p-value will be the primary p-value used to evaluate the result according to the multiple testing strategy described in Section 6.5.

- i. Should the common MH odds ratio from the analysis of at least one of the multiply-imputed datasets be not estimable, combined common MH odds ratio and associated combined common 95% CI and p-value will not be presented. Under such circumstance, conclusions will be based on the p-value obtained from a multiple imputation test of the proportion difference, where the common proportion difference using MH weights and associated common standard errors based on the Sato variance estimator obtained from the analysis of each multiply-imputed dataset will be combined using PROC MIANALYZE based on Rubin's rule.

Similar multiple imputation method will be used for the average weekly WI-NRS and EASI total score.

For the average weekly WI-NRS (refer to Section 5.5), it's the missing average weekly WI-NRS data (i.e., those that cannot be computed because only 3 or less non-missing assessments are available during a given week) at Weeks 1, 2, 3, and 4 that will be multiply imputed, not the missing daily WI-NRS data. Since the missing average weekly WI-NRS values have a precision of 1 decimal place, the MCMC imputation for the non-monotone missing data will be restricted to values between 0 and 10, rounded to the 1st decimal (i.e., 0.1). Imputation of missing data for WI-NRS will be based on the ITT population, i.e., all randomized subjects will be included in the imputation process.

For the EASI total score (refer to Section 5.5), it's the missing EASI total score data at Weeks 1, 2, and 4 that will be imputed, not the missing EASI question score data. Since the missing EASI total scores have a precision of 1 decimal place, the MCMC imputation for the non-monotone missing data will be restricted to values between 0 and 72, rounded to the 1st decimal (i.e., 0.1). Imputation of missing data for EASI total score will be based on the ITT population.

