As the testing sequence progresses, a successful test preserves its assigned alpha as “saved” (“unused” or “accumulated”) alpha that is passed along to the next test in the sequence, as is the case for the sequential method. This accumulated alpha is added to the prospectively assigned alpha (if any) of that next endpoint and the summed alpha is used for testing that endpoint. Thus, as sequential tests are successful, the alpha accumulates for the endpoints later in the sequence; these endpoints are then tested with progressively larger alphas.

[figure not shown]
In this study, the Fallback Method will be applied following this sequence:

Family 1: Testing will proceed at the 0.03 level sequentially within Family 1. Should all 3 endpoints in Family 1 be statistically significant at the 0.03 level, then the full 0.03 alpha will be carried to Family 2. Family 2 would then be tested at the full ($\alpha=0.02+0.03=0.05$).

Should, anywhere during the sequential testing of Family 1, there is a p-value >0.03 , the testing within Family 1 will stop, and no additional alpha can be carried over to Family 2.

	STATISTICAL ANALYSIS PLAN, Version 3.0
Protocol Number: ARQ-151-311	Sponsor: Arcutis Biotherapeutics, Inc.

Figure 2 Multiple Testing Scheme

Achievement of vIGA-AD success is a score of "clear" or "almost clear" plus a 2-grade improvement from baseline.

WI-WRS Success is a 4-point reduction in WI-NRS among subjects ≥ 12 years old with WI-NRS ≥ 4 at baseline.

EASI-75: achievement of at least a 75% reduction in the Eczema Area and Severity Index

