12.1.3 Primary Endpoint Analysis

For the primary analysis, missing vIGA-AD scores will be imputed using multiple imputation as described in Section 6.2.1. These imputations will result in a minimum of 25 to a maximum of 250 complete analysis datasets, depending on the number of imputed monotone datasets that are required.

Percentages of subjects having a vIGA-AD Success (refer to Section 12.1.1) will be presented by visit and treatment group based on multiply imputed data in the ITT population along with a 95% Wilson CI. The common MH odds ratio and common MH proportion difference, adjusted for the randomization factors (i.e., randomized vIGA-AD score and pooled study site) will also be provided along with their common associated 95% CIs. Additionally, count and percentage of subjects having a vIGA-AD success, count and percentage of subjects in each category of the vIGA-AD scale, and descriptive statistics for the vIGA-AD scores, change in vIGA-AD score from

	STATISTICAL ANALYSIS PLAN, Version 3.0
Protocol Number: ARQ-151-311	Sponsor: Arcutis Biotherapeutics, Inc.

baseline and percent change in vIGA-AD score from baseline will be presented by visit and treatment group based on observed data in the ITT population.

The primary endpoint (vIGA-AD Success at Week 4) will then be analyzed using multiple imputation CMH test stratified by the randomization factors. To do so, a CMH analysis will be performed separately for each of the complete multiply imputed analysis data sets, and results will be combined into one multiple imputation inference using the methodology described in Section 6.2.1. Statistical significance will be concluded at the 5% significance level (2-sided). Should the odds ratio be not estimable for at least one multiply imputed dataset, the conclusion of the study will be based on the p-value obtained from a MH test, stratified by the randomization factors, for the common MH proportion difference at Week 4.

The following sensitivity analyses to the primary analysis of the primary endpoint will be performed:

- Multiply-imputed data (refer to Section 6.2.1) on mITT population (refer to Section 4.2) and
- Tipping Point analysis (refer to Section 6.2.3) on ITT population.
- Non-responder imputation (refer to Section 6.2.2) on ITT population.
- Observed data on ITT population (refer to Section 4.1).
- Observed data on PP population (refer to Section 4.3).

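### The imputation seed behind the deciding p-value may be changed after unblinding, with no defined trigger, no named replacement and no rule on which run counts

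*SAP*

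**What the plan says.** SAP 6.2.1 describes a three-step imputation.

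- **Step 1** fills non-monotone gaps by MCMC: "The MCMC method will use the seed 6457149". It produces 1, 3 or 10 datasets when non-monotone missingness is at most 2%, above 2% up to 5%, or above 5%.
- **Step 2** applies predictive mean matching (PMM) with seed 482371: "This process will be repeated 25 times, resulting in a total of 25 to 250 complete analysis datasets". It then states "The seed may be changed after unblinding in case of any issues with the imputation process", with one condition: "it will be documented in the CSR if any change is required".
- **Step 3** runs a CMH analysis on each completed dataset, applies the Wilson-Hilferty transformation and pools by Rubin's rule. Of the result it says: "This p-value will be the primary p-value used to evaluate the result according to the multiple testing strategy described in Section 6.5".

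A similar method is used for the weekly WI-NRS average and the EASI total score. The thresholds are 0.05 for the primary endpoint and the Moderate-subset endpoint, 0.03 for Family 1, and 0.02 for Family 2, rising to 0.05 if all of Family 1 succeeds (SAP 6.5 and 12.1.3).

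Protocol 6.1 states: "The SAP will be finalized before the database is locked and unblinded".

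**The concern.** A plan is finalised before unblinding so that the confirmatory result is determined by the data and rules already written. The step 2 sentence leaves four things open:

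1. what counts as an issue with the imputation;
2. whether only the PMM seed, or also the MCMC seed, may change;
3. what the replacement seed is;
4. which run is confirmatory if the run with the printed seed also completes.

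With few imputations, the pooled p-value still carries Monte Carlo noise. If it lies close to a threshold, the conclusion could rest on a choice made with treatment codes known. The thresholds are also linked: one Family 1 p-value above 0.03 stops that family and leaves Family 2 at 0.02 instead of 0.05, so one seed-dependent result can affect later tests.

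**Working it through.** **Number of datasets.** 25 PMM repeats × 1, 3 or 10 MCMC datasets = 25, 75 or 250, which reproduces the SAP's range. The calculations below take the 25-dataset case.

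**Inputs.** From SAP 5.1: 650 subjects at 2:1 (433/217), 37% vs 22%; and 490 Moderate subjects (327/163), 28% on vehicle plus 17 points = 45%. The documents give no missing-data rate, so FMI is assumed at 2-10%. Subjects who stop for an adverse event or lack of efficacy are fixed non-responders and add no between-imputation variance.

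**Seed-to-seed spread.** SD of the pooled z across seeds = √(FMI/m). With m = 25: √(0.02/25) = 0.028, √(0.05/25) = 0.045, √(0.10/25) = 0.063. Call the p-value that infinitely many imputations would give the limiting p, with normal deviate z. Then 95% of seeds give a p-value within 2·[1 − Φ(z ± 1.96·SD)]:

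| Limiting p | FMI 2% | FMI 5% | FMI 10% |
|---|---|---|---|
| 0.050 | 0.044-0.057 | 0.041-0.061 | 0.037-0.066 |
| 0.030 | 0.026-0.035 | 0.024-0.037 | 0.022-0.041 |
| 0.020 | 0.017-0.023 | 0.016-0.025 | 0.014-0.028 |

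**Chance of landing in the band around 0.05.** The expected z (d), with unpooled variance, is:

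- primary: 0.15 / √(0.37·0.63/433 + 0.22·0.78/217) = 0.15/0.03646 = 4.114;
- Moderate: 0.17 / √(0.45·0.55/327 + 0.28·0.72/163) = 0.17/0.04465 = 3.807.

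Band probability = Φ(1.96 + 1.96·SD − d) − Φ(1.96 − 1.96·SD − d). Over FMI 2-10% this is 0.4-1.0% (primary) and 0.8-1.8% (Moderate). If the SAP's stated 95% and 90% power are taken at face value, d = 1.960 + 1.645 = 3.605 and 1.960 + 1.282 = 3.242, giving 1.1-2.6% and 1.9-4.4%.

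**Chance that one change of seed, made without regard to the result, reverses the conclusion.** With q = Φ((x − 1.96)/SD), this is ∫φ(x − d)·2q(1 − q)dx: 0.13-0.28% (primary) and 0.23-0.52% (Moderate) at the design proportions, or 0.33-0.74% and 0.56-1.25% on the stated power. Each figure is conditional on a change being made.

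**Misuse case, shown for scale only.** If the best of k seeds were kept, type I error = 2∫φ(x)[1 − (1 − Φ((x − 1.96)/SD))^k]dx. At FMI 5% this is 0.050 for k = 1, 0.053 for k = 2, 0.057 for k = 5 and 0.059 for k = 10.

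**Simulation of the SAP's chain** (PMM, stratified CMH, Wilson-Hilferty pooling, m = 25), assuming monotone dropout, 75% Moderate and 5 PMM donors:

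- With 30 pooled sites, dropout of 3%, 5% and 10% gave FMI of 0.03, 0.05 and 0.09, and 95% seed ranges at limiting p 0.05 of 0.043-0.058, 0.042-0.060 and 0.038-0.066. This agrees with the formula.
- With 20 pooled sites and 60 seeds per trial, trials with median p of 0.047-0.054 gave results on both sides of 0.05. One with 10% missing and median 0.048 ranged from 0.032 to 0.071.
- The other thresholds behaved alike: with median p 0.0303, 45% of seeds passed 0.03; with median p 0.0195, 63% passed 0.02.
- Away from the threshold the seed did not matter. All 8 trials with medians of 0.032-0.040 passed 0.05 in 60 of 60 seeds, and medians of 0.060 or more passed in at most 1 of 60.

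**The case against.** The strongest reply is that this is a contingency for technical trouble, written into the plan before unblinding. The text refers to problems with the imputation process and to a change being required; an unwelcome p-value is neither. Both default seeds are printed, so anyone with the data can rerun them, and any change must appear in the CSR. SAP section 1 and Protocol 6.1 also call for departures to be described and justified there. The primary endpoint has non-responder and observed-data analyses that use no seed. In step 2, the seed most naturally means 482371, and a changed seed suggests that the new run replaces the old. The supplied protocol is labelled as the original version, whereas the SAP is based on Amendment 4.

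Much of this stands. The SAP does not license choosing a seed by its result, so the best-of-k figures describe misuse and not the plan. A change made independently of the result leaves type I error at about 0.05. At the planned primary effect the expected z is about 4 and p about 0.0001 or smaller, so a typical result would not depend on the seed.

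It does not remove the point. Disclosure shows a change afterwards; it does not fix the test beforehand. A genuine software failure could already be handled as a justified deviation, so the sentence mainly turns a post-unblinding change into an authorised step. The seed-free analyses are sensitivity analyses and do not decide the test; for the secondary endpoints they are run only if the testing hierarchy allows (SAP 12.2).

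**Conclusion.** The concern holds. The SAP permits an input of the deciding p-value to change after unblinding without a defined trigger, a named replacement or a rule on which run counts. It should be corrected, but it does not threaten the trial at its planned effect.

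The seed matters only for a p-value already near 0.05, 0.03 or 0.02. The probability of that is small for the primary and Moderate endpoints. It cannot be quantified for the other secondary endpoints, because the documents give no expected effects for them.

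The figures rest on an assumed FMI of 2-10% and on 25 datasets built from one MCMC dataset. They do not apply directly where 3 or 10 MCMC datasets are used, or to values filled by the MCMC step. In the simulations, 250 datasets cut the seed-to-seed SD of p near 0.05 to about 0.002, from 0.005-0.009 with 25.

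**What to change.** Delete the sentence and replace it with the following:

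- Seeds 6457149 (MCMC) and 482371 (PMM) are confirmatory whenever the procedure runs to completion.
- A back-up seed may be used only after a named software failure, taken in order from a list fixed in the SAP, with the error log reported. The first listed run that completes is confirmatory.
- Before database lock, the full imputation is dry-run on blinded data with dummy treatment codes, because the PMM model includes treatment group. This cannot guarantee that every failure appears early, which is why the back-up list is still needed.

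Separately, for precision rather than validity, fix a large total number of imputations, for example 500 or more, whatever the non-monotone rate. At FMI 5% the SD of z becomes √(0.05/500) = 0.010, and the seed range at limiting p 0.050 narrows from 0.041-0.061 to 0.048-0.052.

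The cost is SAP wording and minutes of computing time. Data collection does not change.

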6.5 Multiple Comparisons/Multiplicity

To control for familywise type I error at level of 0.05, the secondary endpoint of vIGA-AD Success at Week 4 for subjects with vIGA-AD score of ‘Moderate’ at randomization will only be tested if the primary endpoint demonstrates statistical significance. In addition, the remaining secondary endpoints will be inferentially tested only if the primary and the secondary endpoint (vIGA-AD Success at Week 4 for subjects with vIGA-AD score of ‘Moderate’ at randomization) comparisons are statistically significant using hierarchical testing procedure by partitioning of alpha.

Upon successful demonstration of statistical significance for the primary and above secondary endpoint, the remaining endpoints will be grouped into secondary endpoint family 1, comprised of the 4-point reduction on the WI-NRS endpoint, at Week 4, Week 2 and Week 1, and secondary endpoint family 2, comprised of the endpoints of EASI-75 at Week 4, vIGA-AD of ‘clear’ or ‘almost clear’ at Week 4, vIGA-AD of success at Week 2 and Week 1, vIGA-AD of ‘clear’ or ‘almost clear’ at Week 2 and Week 1. An alpha level of 0.03 will be used to test the endpoints in the secondary endpoint family 1 sequentially. An alpha level of 0.02 will be used to test the endpoints in secondary endpoint family 2 sequentially.

	STATISTICAL ANALYSIS PLAN, Version 3.0
Protocol Number: ARQ-151-311	Sponsor: Arcutis Biotherapeutics, Inc.

In addition to the partitioning of the overall 0.05 alpha into two families, the Fallback Method will be applied. The fallback method is a modification of the fixed-sequence method, providing opportunity to test an endpoint later in the sequence even if an endpoint tested early in the sequence has failed to show statistical significance. The order of the endpoints remains important. The appeal of the fallback method is that if an endpoint later in the sequence has a robust treatment effect while the preceding endpoint is unsuccessful, there is a modest amount of alpha retained as a fallback to allow interpretation of that endpoint without inflating the Type I error rate. Applying the fallback method begins by dividing the total alpha (not necessarily equally) among the endpoints and maintains a fixed sequence for the testing. In this study, the Fallback Method will be applied to the fixed sequence of testing Family 1, and then Family 2.

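### The decision p-value pools a Wilson-Hilferty transform that is slightly liberal at 1 degree of freedom: complete-data size 0.0529, 0.0318 and 0.0211 at nominal 0.05, 0.03 and 0.02

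*SAP*

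**What the plan says.** SAP Section 6.2.1 imputes missing vIGA-AD scores by predictive mean matching (PMM), giving 25 to 250 completed datasets, and runs a stratified CMH test on each. In step 3c, "Two p-values will be produced for each analysis". For the first, the CMH general association statistics "from the analysis of each multiply-imputed dataset will be transformed as per Wilson-Hilferty² before being combined using PROC MIANALYZE" under Rubin's rule, and the p-value is the upper tail of the t distribution. Its role is explicit: "This p-value will be the primary p-value used to evaluate the result according to the multiple testing strategy described in Section 6.5".

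The one exception is a Mantel-Haenszel (MH) odds ratio that cannot be estimated in at least one imputed dataset: "Under such circumstance, conclusions will be based on the p-value obtained from a multiple imputation test of the proportion difference". Section 12.1.3 repeats the exception and sets a two-sided 5% level for the primary endpoint. Sections 12.2 and 12.5 carry the method to the secondary endpoints.

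Section 6.5 sets out its gatekeeping as "To control for familywise type I error at level of 0.05". After the primary endpoint and the moderate-subset endpoint, it splits alpha: "An alpha level of 0.03 will be used to test the endpoints in the secondary endpoint family 1 sequentially", and 0.02 for family 2, which rises to 0.05 if all of family 1 succeeds. Neither section says that the p-value is approximate, and the SAP does not print the Wilson-Hilferty formula.

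**The concern.** Wilson-Hilferty takes the cube root of a chi-square variable to make it roughly normal. The approximation is poorest at low degrees of freedom, and a two-arm binary CMH statistic has just 1. The SAP justifies the one-sided tail by saying that the transform is monotone. That does support using the upper tail, which is not an error: large CMH values arise from differences in either direction. But monotonicity does not make the transformed statistic normal, so the tail area need not equal the chi-square p-value.

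At stake is the stated error rate of a Phase 3 decision. If the transform is liberal at the alpha levels in use, a borderline result could be declared significant although the ordinary CMH test on the same data would not be.

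**Working it through.** **Inputs.** Two arms, 2:1 (SAP 3.1); binary success, hence 1 df; nominal levels 0.05, 0.03 and 0.02 (SAP 6.5). Assumed formula, standard form with SE 1: W = (X^(1/3) − 7/9) / √(2/9), where X is the CMH statistic.

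**Complete data, chi-square reference.** With no between-imputation variance, Rubin pooling returns W with SE 1 and infinite df. The test rejects when X exceeds (7/9 + z(1−α)·√(2/9))³. At α = 0.05 this is (0.7778 + 1.6449 × 0.4714)³ = 1.5532³ = 3.747.

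| Nominal α | Wilson-Hilferty cut-off | Chi-square cut-off | Actual size | Transformed p that would restore α |
|---|---|---|---|---|
| 0.05 | 3.7468 | 3.8415 | 0.0529 | 0.0472 |
| 0.03 | 4.6107 | 4.7093 | 0.0318 | 0.0283 |
| 0.02 | 5.3220 | 5.4119 | 0.0211 | 0.0190 |

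Example: X = 3.80 has chi-square p = 0.0513, but the transformed p is 0.0484. The rule is liberal for exact p above about 0.006 (X below 7.51) and conservative beyond that, so it is liberal at all three levels used.

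**Finite-sample check.** 650 subjects, 2:1, 20 to 40 pooled sites by two severity strata, assumed null response rates of 15–32%, complete data. At nominal 0.05 the ordinary CMH test rejected in 0.0488–0.0501 of trials and Wilson-Hilferty in 0.0517–0.0529.

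**Family split.** If the primary and moderate-subset effects are real and both families are null, the error rate is at most 0.03177 + 0.02106 = 0.0528. If the families were independent it would be 0.0528 − 0.03177 × 0.02106 = 0.0522.

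**Chance that a decision changes.** On complete data this needs an exact p of about 0.050–0.053, 0.030–0.032 or 0.020–0.021. At the 0.05 gates it is P(1.9357 < Z < 1.9600):
- At the stated power: 0.25% (primary, 95%) and 0.42% (moderate subset, 90%).
- At the power that the rates in SAP 5.1 imply (unstratified normal approximation, no dropout): 0.12% and 0.20%. These use 97.9% for 37% vs 22% in 433/217 subjects, and 96.0% for 45% vs 28% in 327/163.

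**With imputation.** Null simulation of PMM plus the composite non-responder rule, nominal 0.05:

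| Missing (assumed) | Wilson-Hilferty | Signed root, two-sided t | Pooled log MH odds ratio | MH difference, Sato variance |
|---|---|---|---|---|
| None | 0.0532 | 0.0501 | – | – |
| 5% | 0.0506 | 0.0476 | 0.0465 | 0.0481 |
| 10% | 0.0475 | 0.0449 | 0.0436 | 0.0463 |
| 20% | 0.0419 | 0.0399 | 0.0383 | 0.0410 |

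There were 37,000 trials at 5% (also used for the complete-data row) and 50,000 each at 10% and 20%; Monte Carlo SE is about 0.001. Assumptions:
- 32 pooled sites, 75% moderate, Week 4 success of 28% (moderate) and 4% (mild) in both arms.
- Latent correlation of 0.75 between adjacent visits and 0.55 between Weeks 1 and 4.
- Monotone dropout completely at random, 30% of it for adverse event or lack of efficacy.
- 5 PMM donors and 25 imputations.

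The paired excess of Wilson-Hilferty over the signed root was 0.0030, 0.0027 and 0.0020 at 5%, 10% and 20%. At 10% and 20%, every disagreement was a rejection by Wilson-Hilferty alone (133 and 98 of 50,000, against none the other way).

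Two simpler imputation models gave higher totals. Beta-posterior imputation within arm and severity gave Wilson-Hilferty 0.0525–0.0530 and signed root 0.0498–0.0503 at 5–20% missing. Idealised Rubin pooling with 25 imputations and missing-information fractions of 0.01–0.30 gave about 0.053–0.055 and 0.050–0.052.

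**The case against.** The strongest reply is that the headline sizes apply only when imputation adds no variance, whereas the SAP plans for missing data. In the simulation closest to the planned procedure, Wilson-Hilferty at 5% missing is within Monte Carlo error of 0.05, and at 10–20% it is below. The models disagree on total size once data are missing, so only the complete-data figures are settled. That stands, and it is why the point is limited to few missing data. But the low totals come from Rubin's variance being conservative there, not from an accurate transform. An offset of unknown size does not guarantee error control.

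It can also be said that the plan already shows enough to expose a discrepancy. It has the proportion-difference p-value, pooled confidence intervals, and the non-responder and observed-data CMH analyses in Section 12.1.3, which need no transform. These would reveal a borderline case, but they do not decide it.

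Lastly, the signed root is itself approximate under Rubin pooling, and with 10–20% missing it moves the PMM procedure further below 0.05. Both are true. The second is a real, if small, cost. The formula and the chi-square reference are assumptions too.

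**Conclusion.** The point holds. Given the standard 1-df formula and a chi-square reference, the decision p-value has complete-data size 0.0529, 0.0318 and 0.0211 at nominal 0.05, 0.03 and 0.02. The familywise control at 0.05 in Section 6.5 and the 5% level in Section 12.1.3 are therefore only approximate when few data are missing. With more missing data, total size depends on the imputation model, and the documents give no missing rate. In every model tried, the transform still rejected more often than the signed root.

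The practical effect is small: well under a 1% chance of altering either 0.05-level decision at the planned power. It is worth correcting because it concerns the decision test and is cheap to correct, not because the trial's conclusion is in serious doubt.

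**What to change.** For the decision p-value, take the signed square root of each dataset's CMH statistic, with the sign of observed minus expected successes on active and variance 1. Pool by Rubin's rules and use the two-sided t p-value. This keeps the same stratified CMH test and removes the transform's own error. Leave the proportion-difference fallback as written.

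If Wilson-Hilferty is kept, print the formula in Section 6.2.1, call the control in Section 6.5 approximate with the complete-data size of 0.0529, and report the signed-root p-value beside it. A Wald test of the pooled log MH odds ratio from step 3a is a weaker alternative. It would be a newly specified decision test, ran more conservatively in the PMM simulation, and would still need the fallback.

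The cost is a few lines of SAP text and SAS code before unblinding. Borderline p-values become slightly larger. At 10–20% missing, rejection under the null falls by a further 0.002–0.003 in the PMM simulation.
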